7.0 CLINICAL MANAGEMENT ISSUES

7.1 Toxicity

Only toxicities related to study medications will be considered in the toxicity management section. The grading system for drug toxicities is located in the DAIDS AE Grading Table, Version 1.0, December 2004 (Clarification, August 2009), located at the DAIDS RSC web site: <http://rsc.tech-res.com/clinical-research-sites/safety-reporting/daids-grading-tables>.

7.1.1 Grade 1

Study participants who develop a Grade 1 AE or toxicity may continue study medications at the discretion of the site investigator.

If participants choose to discontinue study drug, the A5312 Clinical Management Committee ([contact]) should be notified within 48 hours. The site should complete the premature discontinuation evaluations, as per [section 6.1.2](#), within 7 days after stopping study medications.

7.1.2 Grade 2

Participants who develop a Grade 2 AE or toxicity may continue study drugs, at the discretion of the site investigator, and will be followed carefully.

If participants choose to discontinue study drug, the A5312 Clinical Management Committee should be notified within 48 hours. The site should complete the premature discontinuation evaluations, as per [section 6.1.2](#), within 7 days after stopping study medications.

Grade 2 clinical or laboratory abnormalities that are deemed likely related to study drug will be followed to stabilization or resolution to Grade ≤ 1 . Evaluations and the frequency of follow-up visits are at the discretion of the site investigator. The A5312 Clinical Management Committee should be notified of any requirements for continuing follow-up of toxicities beyond 7 days after stopping study medications.

7.1.3 Grade 3

Unless the site investigator has compelling evidence that the Grade 3 AE or toxicity is not related to the study drug, the participant must permanently discontinue the study drug. The A5312 Clinical Management Committee should be notified within 48 hours. The site should complete the premature discontinuation evaluations, as per [section 6.1.2](#), within 7 days after stopping study medications.

Clinical or laboratory abnormalities of Grade 3 that are deemed likely related to study medication will be followed to stabilization, resolution to Grade ≤ 1 , or return to baseline. Evaluations and the frequency of follow-up visits are at the discretion of the site investigator. The A5312 Clinical Management Committee should be notified of any requirements for continuing follow-up of toxicities beyond 7 days after stopping study medications.

7.1.4 Grade 4

Any participant with Grade 4 toxicity will be immediately and permanently discontinued from the study. The site should complete the premature discontinuation evaluations, as per [section 6.1.2](#), within 7 days after stopping study medications.

Clinical or laboratory abnormalities of Grade 4 that are deemed likely related to study medication will be followed to stabilization, resolution to Grade ≤ 1 , or return to baseline. Evaluations and the frequency of follow-up visits are at the discretion of the site investigator. The A5312 Clinical Management Committee should be notified of any requirements for continuing follow-up of toxicities beyond 7 days after stopping study medications.

7.2 Other Diseases

Participants who develop new medical diagnoses during the study will be counseled and given recommendations for referrals to medical providers, as necessary.

7.3 Pregnancy

After study entry, female participants who become pregnant must immediately discontinue study treatment and complete the premature study discontinuation evaluations. They will be referred to their local clinic for standard TB care and prenatal care. Site personnel must notify the A5312 Clinical Management Committee ([contact]) within 48 hours after receiving this information. Pregnancy outcomes will not be recorded.

8.0 CRITERIA FOR DISCONTINUATION

8.1 Premature Study Discontinuation

- Inability to produce an overnight sputum sample of sufficient quality and quantity over a 16-hour collection period on Step 2 Day 0
- Grade ≥ 3 drug-related AE or toxicity or any Grade 4 AE or toxicity (see [section 7.1](#) Toxicity)
- Requirement for prohibited concomitant medications (see [section 5.4](#))
- Failure by the participant to comply with inpatient hospital stay
- Pregnancy

- Nonadherence with one or more doses of study treatment
- Development of another medical condition that makes the administration of one or more planned doses of study drug inadvisable
- Inability to provide a study-required sputum sample at any time through day 8
- Request by the participant to stop study treatment or withdraw
- It is the investigator's judgment that it is no longer in the best interest of the participant to continue study participation.
- At the discretion of the ACTG, IRB/EC, NIAID, Office for Human Research Protections (OHRP), or other government agencies as part of their duties, or the investigator.

9.0 STATISTICAL CONSIDERATIONS

9.1 General Design Issues

This is a two-stage, two-step, phase IIa, open-label EBA and PK study in participants with sputum smear-positive pulmonary TB.

No study drug is administered under Step 1. Data collected in Step 1: (a) determine eligibility to Step 2, and (b) allow characterization of INH MICs in 3 groups (secondary objective). Groups 1, 2, and 3 consist of participants infected with TB with *inhA* mutations, with DS-TB, and with TB with *katG* (with or without an *inhA* mutation) resistance-conferring mutations, respectively.

The study's primary objectives are addressed via Step 2 evaluations, through which the study estimates the 7-day EBA of INH among participants infected with TB with *inhA* mutations (Group 1) taking one of three doses of INH (5, 10, or 15 mg/kg), **participants infected with TB with *katG* with or without *inhA* mutations (Group 3) taking 15 or 20 mg/kg of INH (TTP only)**, and participants infected with DS-TB (Group 2) taking standard-dose INH (5 mg/kg daily). In addition, the association between PK parameters, such as AUC/MIC, and the EBA of INH will be examined. The total sample size for determination of participant-specific EBAs is set to **84** evaluable participants at minimum.

The study will be conducted in two stages: Stage 1 is a feasibility pilot to ensure that recruitment can proceed at a reasonable pace and also to examine whether the estimate of SDs for the sample size calculations are reasonable. During Stage 1, 15 Group 1 participants will be enrolled to Step 2, and they will be randomized 1:1:1 to a dose of 5, 10, or 15 mg/kg of INH daily. During Stage 2, 33 additional participants in Group 1 will be randomized 1:1:1 to 5, 10, or 15 mg/kg until the accrual target of evaluable participants is reached.

During Stage 1, which closed to accrual on March 26, 2015, 44 Group 2 participants enrolled to Step 1 only; these participants did not receive any study drug, but had sputum collected for MIC determination. During Stage 2, 16 participants in Group 2 who meet the Step 2 entry criteria will enter Step 2 and will be assigned to receive 5 mg/kg

daily (positive control). In addition, if the accrual target for Group 2, “Step 1 only” has not yet been met and the Group 2 participant does not meet Step 2 eligibility criteria, they may also enroll to Step 1. **During Stage 2, 20 participants in Group 3 who meet the Step 2 entry criteria will enter Step 2 and will be randomized 1:1 to receive 15 or 20 mg/kg of INH daily. In addition, if the accrual target for Group 3 “Step 1 only” has not yet been met and Group 3 participants do not meet Step 2 eligibility criteria, they may also enroll to Step 1.**

During Stages 1 and 2 combined, the maximum number of participants in Groups 1, 2, and 3 enrolling to **Step 1 only are 70, 64, and 84, respectively.**

9.2 Endpoints

9.2.1 Primary Endpoints

- 9.2.1.1 Daily decline in \log_{10} CFU per mL sputum from baseline to Day 7 of study treatment, defined as EBA_{0-7} (CFU) = [baseline \log_{10} CFU per mL (mean of the pre-entry visit and entry visit sputum colony counts) – Day 7 \log_{10} CFU per mL]/7 (**Groups 1 and 2**)
- 9.2.1.2 Daily decline in TTD from baseline to Day 7 of study treatment, defined as EBA_{0-7} (TTD) = [baseline TTD (mean of the pre-entry visit and entry visit TTDs) – Day 7 TTD]/7 (**all groups**).
- 9.2.1.3 Daily \log_{10} CFU per mL sputum and TTD from baseline to Day 7 of study treatment; area under the time-concentration curve (AUC) for INH; MIC of *M. tuberculosis* isolates against INH (**Group 1 for CFU and TTD and Group 3 for TTD only**)
- 9.2.1.4 Grade 2 or higher drug-related adverse clinical or laboratory events (**all groups**)

9.2.2 Secondary Endpoints

- 9.2.2.1 Steady state PK parameters, including maximum concentration (C_{max}), AUC_{0-24} , and $T_{1/2}$; NAT2 acetylator status (See Section 10.0) (**all groups**). All PK parameters will be measured from the PK sampling at Day 6 and NAT2 acetylator status will be determined based on specimens collected at Step 2 Day 0.
- 9.2.2.2 INH MIC against *M. tuberculosis* isolates as determined by phenotypic DST (all groups). INH MIC will be determined from spot sputum collected at Step 1 Day 0.
- 9.2.2.3 AUC/MICs which reach 50% of the mean EBA_{0-7} (CFU) and EBA_{0-7} (TTD) among Group 2 participants (**Group 1 for CFU and TTD and Group 3 for TTD only**). INH MIC will be determined from spot sputum

collected at Step 1 Day 0 and AUC will be measured from the PK sampling at Day 6.

9.2.2.4 The endpoints below are created separately based on \log_{10} CFU and TTD.

If the number of phases is the same for every dosing **cohort**:

- EBA measured by early- and late-phase individual-based parameter estimates from nonlinear mixed effect models. The early- and late-phase slopes are denoted as EBA_{0-2} and EBA_{2-7} , respectively. Before fitting the model, both TTDs and \log_{10} CFU from the pre-evaluation and entry visits will be averaged and treated as the baseline TTD and \log_{10} CFU (**all groups**).

If the number of phases differs between every dosing **cohort**:

- EBA measured by individual-based parameter estimates from linear or nonlinear mixed effect models. Before fitting the model, both TTDs and \log_{10} CFU from the pre-evaluation and entry visits will be averaged and treated as the baseline TTD and \log_{10} CFU.
- (\log_{10} CFU only) EBA measured by ratio of the following areas: numerator = AUC of observed \log_{10} CFU over 7 days and denominator = baseline \log_{10} CFU for each **participant**.

9.2.3 Exploratory Endpoints

9.2.3.1 Daily TTD and \log_{10} CFU per mL sputum between baseline and Day 7. Both TTDs and \log_{10} CFU from the pre-evaluation and entry visits will be averaged and treated as the baseline TTD and \log_{10} CFU.

9.2.3.2 NAT2 genotype results from the new PCR method using saliva sample; NAT2 genotype results from standard methods that use sequencing using whole blood sample. NAT2 acetylator status will be determined based on specimens collected at Step 2 Day 0.

9.2.3.3 MTBDRs/ result (i.e., binary resistance status of quinolone **and aminoglycoside**) based on sputum collected at Step 2 Day 0.

9.3 Randomization and Stratification

No randomization takes place under Step 1. Participants in Groups **1 and 3** who are eligible for Step 2 will be randomized equally to the three **and two** doses, **respectively**. During Stage 2, participants in Group 2 who are eligible for Step 2 will be enrolled at a pace to try to keep enrollments into each dosing cohort about equal (on average enroll two Group 1 participants into Step 2, then one Group 2 participant into Step 2, etc.) by setting a recruitment limit for Group 2. The data manager and statisticians will manually adjust the limit routinely (e.g., every month or twice per month). Randomization will not be stratified.

9.4 Sample Size and Accrual

Primary Objectives:

One of the primary objectives is to estimate the distribution of the EBA_{0-7} (CFU) from each cohort in Group 1 (5, 10, and 15 mg/kg of INH for participants with an *inhA* mutation) and the EBA_{0-7} (CFU) from Group 2 (5 mg/kg of INH for participants without *katG* or *inhA* mutations). **Another primary objective is to estimate the distribution of the EBA_{0-7} (TTP) from each cohort in Group 1, Group 2, and each cohort in Group 3.** The aim is to establish proof-of-concept for the higher doses of INH.

Sample Size:

The planned sample size is 16 participants per treatment **cohort in Group 1 and Group 2**; participants discontinuing before the day 7 sample collection will be replaced. This sample size is similar to that of other recent exploratory EBA studies.

Here is some information about the likely precision of estimates that can be achieved with the planned sample size of 16 participants in this proof-of-concept study. Among participants with DS-TB who were taking 300 mg doses of INH, the estimated mean EBA_{0-5} was $0.21 \log_{10}\text{CFU/mL/day}$ ($n=16$, SE 0.03, between-participant SD 0.12, coefficient of variation [CV] 57%) [41]. We assume the mean EBA_{0-7} (CFU) from Group 1 is approximately half of EBA_{0-7} (CFU) from Group 2. Further assuming constant CV, the table below gives the anticipated precisions (half-widths) of 95% confidence intervals (CIs) around estimates of $\log_{10}\text{CFU/mL/day}$ for any one Group 1 cohort and for the Group 2 cohort, for sample sizes of 10, 16, and 20. Because the MIC distribution may be more variable for Group 1, the table also shows anticipated CI widths for a Group 1 cohort if the CV and SD are larger (114% and 0.120, respectively).

Table 9.4-1: Sample Size per Arm and Expected Half-width of 95% CI for the Hypothesized Mean \log_{10} CFU/mL Decrease per Day with a Range of Estimated CV and SD

Group	Sample Size per Group	Hypothesized Mean \log_{10} CFU/mL/day	CV	SD	Expected Half-width of 95% CI
Any one Group 1 cohort	10	0.105	57%	0.060	0.043
	16	0.105	57%	0.060	0.032
	20	0.105	57%	0.060	0.028
Any one Group 1 cohort	10	0.105	114%	0.120	0.086
	16	0.105	114%	0.120	0.064
	20	0.105	114%	0.120	0.056
Group 2	10	0.210	57%	0.120	0.086
	16	0.210	57%	0.120	0.064
	20	0.210	57%	0.120	0.056

For Group 1 cohorts, the sample size of 16 is required for a two-sided 95% CI with a precision (half-width) of less than or equal to 0.064 with SDs between 0.060 and 0.120. This means that, for example, if the mean of EBA₀₋₇ (CFU) from the 15 mg/kg of INH for participants with an *inhA* mutation is 0.1 and the SD is 0.12, there is 95% probability that the CI of 0.04 and 0.17 covers the true mean.

Similarly, if the mean of EBA₀₋₇ (CFU) from Group 2 is 0.2 and the SD is 0.12, there is 95% probability that the CI of 0.14 and 0.26 covers the true mean.

This sample size should allow for evaluation of the association between AUC/MIC and EBA₀₋₇, one of the other primary analyses, with high precision, as the data from all experimental dosing cohorts will be pooled for this PK/PD analysis [9, 13, 15, 42].

For Group 3, the sample size of 10 per dosing cohort was selected since the analysis of EBA₀₋₇ (TTP) per dosing cohort will be exploratory. Assuming the SD for Group 3 cohorts will be 6, which is the overall SD of EBA₀₋₁₄ (TTP) from the previous ACTG EBA study (A5307, unpublished), a half-width of a 95% CI is 0.086 with the sample size of 10. This means, for example, if the mean of EBA₀₋₇ (TTP) from a dosing cohort in Group 3 is 13, there is 95% probability that the CI of 9.28 and 16.7 covers the true mean. A possible dosing effect for this group will be examined through visual displays.

Accrual:

During Stage 1, five participants were recruited to each cohort in Group 1. During Stage 2, 11 additional participants will be recruited to each cohort in Group 1, **20 participants in Group 3**, and 16 participants in Group 2 will be recruited. In the final analyses, the data from both stages will be combined. The time to accrual for this study (Stage 1 and 2 combined) is approximately **4 years**.

To maintain desired precision of estimation (primary analyses), participants who discontinue the study prior to the Day 7 evaluations will be replaced. All data from every randomized participant will be stored in the study database, and will be examined for the final analyses.

Participants enrolling to Step 1 only will be considered evaluable if all data that are required are available at screening and/or entry regardless of subsequent known or unknown loss to follow up.

Table 9.4-2: A5312 Accrual Targets

	Resistance Mutation	Participants Completing Step 1 Only ¹	Participants Completing Step 1 and Step 2 ²		Total Participants
		Stage 1 & Stage 2 Combined	Stage 1	Stage 2	
Group 1	inhA	Minimum of 16 to a maximum of 70 ³	15 (5 per dosing cohort)	33 (11 per dosing cohort)	Step 1 only: maximum of 70 ³ Steps 1 and 2: 48
Group 2	Neither inhA nor katG	Minimum of 48 to a maximum of 64 ⁴	-	16	Step 1 only: maximum of 64 ⁴ Steps 1 and 2: 16
Group 3	katG with or without inhA	Minimum of 64 to maximum of 84	-	20 (10 per dosing cohort)	Step 1 only: maximum of 84⁵ Steps 1 and 2: 20

¹ Participants completing Step 1 only (participants who were considered for Step 2 but could not enter Step 2, or participants who were considered for Step 1 only) will provide sputum for determination of MIC distribution, and then be discontinued from the study.

² Participants completing Step 1 and Step 2 will provide sputum for determination of MIC distribution and participate in the treatment part of the study.

³ Once the Group 1 accrual target is reached for participants completing Steps 1 and 2, accrual beyond the minimum for those completing Step 1 only will stop.

⁴ Once the Group 2 accrual target is reached for participants completing Steps 1 and 2, accrual beyond the minimum for those completing Step 1 only will stop.

⁵ **Once the Group 3 accrual target is reached for participants completing Steps 1 and 2, accrual beyond the minimum for those completing Step 1 only will stop.**

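### Protocol 9.4 states a Group 3 confidence-interval half-width of 0.086 that SD 6 and n=10 cannot give; by the protocol's own t method it is 4.29

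*Protocol*

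**What the plan says.** Section 9.4 of the protocol gives one quantitative precision statement for Group 3. It begins "Assuming the SD for Group 3 cohorts will be 6", and names the source of that value as the overall SD of a 14-day EBA (EBA0-14) in an earlier, unpublished study. It then states that "a half-width of a 95% CI is 0.086 with the sample size of 10". The next sentence takes a mean EBA0-7 that "from a dosing cohort in Group 3 is 13" and says "there is 95% probability that the CI of 9.28 and 16.7 covers the true mean". No unit is given.

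The reason for the cohort size comes just before: "the sample size of 10 per dosing cohort was selected" because the per-cohort analysis is to be exploratory.

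Table 9.4-1 in the same section gives half-widths for Groups 1 and 2 on the log10 CFU/mL/day scale. One of its Group 1 rows reads "10 0.105 114% 0.120 0.086": n, mean, CV, SD and half-width. The SAP neither repeats nor corrects the Group 3 figures.

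**The concern.** The two Group 3 sentences cannot both be right. One gives a half-width of 0.086; the other shows an interval that extends about 3.7 on each side of the mean.

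The figure describes an endpoint that matters for this group. CFU counts are done for Groups 1 and 2 only (Protocol 6.3.9 and 9.2.1), so EBA0-7 (TTD) is the only primary EBA endpoint in Group 3. SAP 4.3.1 plans a plot of its 95% confidence interval by cohort. Hypothesis 1.1.3 is that 15 or 20 mg/kg has measurable activity against katG strains. Taken at face value, 0.086 suggests that almost any nonzero cohort mean could be told apart from zero. With the correct figure the mean would have to exceed about 4.3 in magnitude, which changes how a small or null result should be read.

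**Working it through.** **Inputs (Protocol 9.4).** SD 6; n=10 per cohort; 95% level, two-sided as stated for Group 1; example mean 13. Participants who leave before Day 7 are replaced, so n stays at 10. Section 9.4 writes TTP where Section 9.2 writes TTD; I treat them as the same measure.

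**Formula.** Half-width = multiplier × SD/√n, with multiplier t(0.975, n−1) or z = 1.96.

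**Step 1: which multiplier the protocol uses.**

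| SD | n | Stated | t | z |
|---|---|---|---|---|
| 0.060 | 10 | 0.043 | 0.0429 | 0.0372 |
| 0.060 | 16 | 0.032 | 0.0320 | 0.0294 |
| 0.060 | 20 | 0.028 | 0.0281 | 0.0263 |
| 0.120 | 10 | 0.086 | 0.0858 | 0.0744 |
| 0.120 | 16 | 0.064 | 0.0639 | 0.0588 |
| 0.120 | 20 | 0.056 | 0.0562 | 0.0526 |
| 0.120 | 22 | 0.053 (Section 9.5) | 0.0532 | 0.0501 |
| 6 (Group 3) | 10 | 0.086 | 4.29 | 3.72 |

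All the CFU half-widths reproduce with t and none with z.

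**Step 2: the Group 3 half-width.**
- Two-sided t: 2.262 × 6/√10 = 4.29.
- z: 1.96 × 6/√10 = 3.72.
- One-sided t: 3.48.

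None is near 0.086. With t and n=10, 0.086 implies an SD of 0.086 × √10/2.262 = 0.120, which is the SD in the CFU row quoted above. At SD 6 it would need about (1.96 × 6/0.086)² ≈ 18,700 participants.

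**Step 3: the example interval.** With z, 13 ± 3.72 gives 9.28 to 16.72, which is the stated interval after rounding. With t, 13 ± 4.29 gives 8.71 to 17.29.

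**Step 4: size of the discrepancy.** 4.29/0.086 ≈ 50, and 4.29/3.72 ≈ 1.15.

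**Step 5: unit.** Section 6.3.9 measures TTD in hours, and the endpoint divides by 7 days, so the unit is hours/day. As a check, a mean of 13 per day is a change of 13 × 7 = 91 over the week. In hours that is under four days. In days it would be more than twice the 42-day TTD that SAP 3.2 calls rare.

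**Step 6: dependence on the SD.** At n=10 the t half-width is 2.262/√10 = 0.715 times the SD. For illustration, SDs of 4, 6, 8 and 12 give 2.9, 4.3, 5.7 and 8.6.

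**The case against.** The strongest defence is that little depends on 0.086. The example beside it is on the right scale, so an attentive reader would see the slip. If the SD of 6 is taken as known, z is legitimate and 9.28 to 16.7 is arithmetically correct. Both that interval and the t-based one exclude zero. No test, threshold or decision rule uses the figure. All of this stands, and it limits the consequence. It does not rescue 0.086, and it leaves the example out of line with the method behind every other half-width in the protocol.

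Three stronger readings are tempting, and the documents do not support them.

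- A reader might infer that n=10 has lost its only justification. Section 9.4 rests n=10 on the exploratory nature of the per-cohort analysis; the half-width only illustrates that choice.
- A reader might infer that the planned intervals will under-cover. A z interval built on an SD estimated from 10 participants would cover about 91.8%, but no such interval is planned. SAP 4.3.1 asks for a 95% confidence interval for the mean and names no multiplier.
- A reader might infer that the 7-day SD must exceed 6, because sample noise in a two-point EBA is divided by fewer days. If noise were the whole variance and the earlier EBA was also two-point, the SD would double to 12. The documents do not show that study's design or noise share. An overall SD may also pool across arms and so exceed a within-cohort SD. Section 9.4 borrows across windows for CFU too, from a 5-day EBA. The fair statement is that the 7-day SD is uncertain in either direction.

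**Conclusion.** The Group 3 half-width is wrong as written. With the protocol's SD of 6, n=10 and its usual t multiplier it is 4.29 hours/day, about 50 times the stated 0.086. The example interval should be 8.71 to 17.29; the stated one is about 13% narrower (3.72 against 4.29). That 0.086 came from the CFU table is an inference from an exact match, and the error does not depend on it.

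The failure of 0.086 needs no assumption beyond the stated SD and n. The value 4.29 rests on using t, as the protocol does elsewhere, and on the borrowed SD of 6 holding for a 7-day EBA. The sample size and the planned analysis are unaffected. What changes is the documented expectation of what a cohort of 10 can show.

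**What to change.** In Protocol 9.4:

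- Replace 0.086 with 4.29 and the example interval with 8.71 to 17.29, and say that the t multiplier is used as in Table 9.4-1.
- Give the unit as hours/day.
- Keep the disclosure that the SD of 6 comes from a 14-day EBA. Add that the 7-day SD may be lower or higher and that the half-width is about 0.715 × SD, with 2.9, 4.3, 5.7 and 8.6 for SDs of 4, 6, 8 and 12 as illustrations.
- Keep n=10 per cohort and its stated rationale.

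The cost is a wording correction in one paragraph, with no added participants and no change to the analysis. The stated precision becomes less favourable. If the protocol is not amended again, the corrected figures can go in a clarification memo or in the report on the Version 3.0 participants.

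### Protocol 9.4 gives Group 3 a 95% CI half-width of 0.086, but SD 6 and n = 10 give 4.29 (t) or 3.72 (z), and the next sentence's interval contradicts 0.086

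*Protocol*

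**What the plan says.** The Group 3 paragraph of Protocol 9.4 makes four statements in sequence.

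- Size: "the sample size of 10 per dosing cohort was selected" because the per-cohort TTP analysis is regarded as exploratory. Any dose effect is to be looked at graphically.
- SD: "Assuming the SD for Group 3 cohorts will be 6". The value is the overall SD of a 0 to 14 day EBA (TTP) "from the previous ACTG EBA study (A5307, unpublished"). No unit is printed.
- Precision: "a half-width of a 95% CI is 0.086 with the sample size of 10".
- Illustration, introduced as following from that precision: if the mean "from a dosing cohort in Group 3 is 13", then "there is 95% probability that the CI of 9.28 and 16.7 covers the true mean".

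The preceding Table 9.4-1 ("Sample Size per Arm and Expected Half-width of 95% CI for the Hypothesized Mean" log10 CFU/mL decrease per day) covers Groups 1 and 2 only. At n = 10 it gives 0.043 for SD 0.060 and 0.086 for SD 0.120. Protocol 9.5 gives a half-width of at most 0.053 at n = 22 for SDs up to 0.120.

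EBA0-7 (TTD) is a primary endpoint for all groups (Protocol 9.2.1.2), and SAP 4.3.1 plans a 95% CI for each cohort mean. SAP 2.1 repeats 10 per arm without a precision figure. Neither Version 3.0 clarification memo nor the SAP corrects the statement.

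**The concern.** A half-width follows directly from the SD, the sample size and the quantile, and all three can be read from the protocol. With an SD of 6 and ten participants, the standard error alone is 6/√10 = 1.90, so a half-width of 0.086 is not possible. The illustration in the next sentence has a half-width more than 40 times larger than the figure it is meant to illustrate.

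What is at stake is what a reader believes ten participants per cohort will deliver. Set against an example mean of 13, a half-width of 0.086 suggests an almost exact estimate. The correct figure of about 4.3 is a third of that mean. Protocol 9.4 is the only place in either document that states the expected precision for Group 3, the treatment cohort added in Version 3.0.

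**Working it through.** **Inputs (all from Protocol 9.4 unless noted).** SD 6; n = 10; 95% two-sided; stated half-width 0.086; example mean 13; example interval 9.28 to 16.7. For comparison: Table 9.4-1, and the n = 22 figure in Protocol 9.5.

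**Formula.** Half-width = q × SD/√n, with q = 1.960 (normal, z) or q = t(0.975, n − 1), which is 2.262 for n = 10.

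**Step 1. Which quantile does the plan use elsewhere?**

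| SD | n | Printed | t | z |
|---|---|---|---|---|
| 0.060 | 10 | 0.043 | 0.0429 | 0.0372 |
| 0.060 | 16 | 0.032 | 0.0320 | 0.0294 |
| 0.060 | 20 | 0.028 | 0.0281 | 0.0263 |
| 0.120 | 10 | 0.086 | 0.0858 | 0.0744 |
| 0.120 | 16 | 0.064 | 0.0639 | 0.0588 |
| 0.120 | 20 | 0.056 | 0.0562 | 0.0526 |
| 0.120 | 22 (Section 9.5) | 0.053 | 0.0532 | 0.0501 |

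The SD 0.120 rows for n = 10, 16 and 20 appear twice in the table (Group 1 with the larger CV, and Group 2), so all nine cells are covered. Every one matches t and none matches z. The n = 22 figure also matches t only.

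**Step 2. Group 3 as stated (SD 6, n = 10).**

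- t: 2.262 × 6/√10 = 4.29; ratio to the stated value 4.292/0.086 = 49.9.
- z: 1.960 × 6/√10 = 3.72; ratio 3.719/0.086 = 43.2.

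**Step 3. Could another reading give 0.086?** Half-widths at SD 6 unless noted:

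| Variant | z | t |
|---|---|---|
| 90% level | 3.12 | 3.48 |
| Both cohorts pooled, n = 20 | 2.63 | 2.81 |
| SD divided by 7 | 0.53 | 0.61 |
| SD divided by 14 | 0.27 | 0.31 |
| SD divided by 24 | 0.15 | 0.18 |
| SD divided by 168 | 0.022 | 0.026 |

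None gives 0.086. At SD 6, that half-width would need n = (1.960 × 6/0.086)², about 18,700.

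**Step 4. Where might 0.086 come from?** Solving for the SD at n = 10 with t: 0.086 × √10/2.262 = 0.120. That is the log10 CFU SD in Table 9.4-1, whose n = 10 entry is 0.086. Group 3 has no CFU endpoint (Protocol 9.2.1.1).

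**Step 5. The printed interval.** (16.7 − 9.28)/2 = 3.71.

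- z: 13 ± 3.72 = 9.28 to 16.72, which is the printed interval to three significant figures.
- t: 13 ± 4.29 = 8.71 to 17.29.

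The t half-width is 4.292/3.719 = 1.15 times the z half-width.

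**Step 6. Unit and sign.** Protocol 6.3.9 has TTD measured in hours, and Protocol 9.2.1.2 defines the endpoint as (baseline − Day 7)/7. The unit is therefore hours per day, if the SD of 6 is on that scale. Under that definition a lengthening TTD gives a negative value, whereas the example mean is +13.

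**The case against.** The strongest reply is that nothing downstream uses 0.086. The protocol chose ten per cohort because the analysis is exploratory, the half-width only illustrates that choice, and the SAP will compute intervals from the observed data. The adjacent interval also has the right order of magnitude, so an attentive reader is not left with only the wrong number. All of this stands. It limits the consequence but does not rescue the figure.

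On the quantile, a normal interval for an assumed SD is a common planning approximation. That also stands, so the mismatch with Table 9.4-1 is a matter of consistency. The worked examples for Groups 1 and 2 do not settle which quantile was meant. The Group 2 interval (0.14 to 0.26) rounds the same either way. The Group 1 interval (0.04 to 0.17) fits neither around the printed mean of 0.1 and fits t around 0.105. The evidence for t is the table and Section 9.5.

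Four stronger readings are tempting, and the documents do not support them:

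- That the Group 3 sample size rests on 0.086. The stated reason is the exploratory purpose.
- That 0.086 is the only precision information for Group 3. The example interval conveys about 3.7.
- That the final Group 3 intervals will under-cover. A 1.96 multiplier with an SD estimated from ten people would cover 91.8%, but SAP 4.3.1 specifies 95% intervals without committing to 1.96.
- That the figure is wrong for any SD. It is right for 0.120; it is wrong because the stated SD is 6.

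**Conclusion.** The concern holds as an error in a stated precision figure and a contradiction between adjacent sentences. Given the protocol's own SD of 6 and n of 10, the half-width is 4.29 on the t basis used in Table 9.4-1, or 3.72 on the normal basis. The printed 0.086 is too small by a factor of 49.9 or 43.2. Carry-over from the CFU table is the likely explanation, but it remains an inference.

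The normal-based interval is a secondary inconsistency: the t half-width is 15% wider. The sample size, the endpoint and the planned analysis are unaffected.

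The corrected values take the SD of 6 as given. It comes from a 0 to 14 day EBA, is applied to a 0 to 7 day EBA and has no printed unit. The documents offer nothing further to support that transfer.

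**What to change.** In the Group 3 paragraph of Protocol 9.4:

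1. Replace 0.086 with 4.29 and the example interval with 8.71 to 17.29, which matches the t basis of Table 9.4-1. Alternatively, state that the normal quantile is used and print 3.72 with 9.28 to 16.72.
2. Name the unit: hours per day, once it is confirmed that the SD of 6 is on that scale.
3. Align the sign of the example mean with the definition in Protocol 9.2.1.2 (baseline minus Day 7), or state that the example refers to the increase in TTD.
4. If the SD assumption is revised, recompute with the same formula.

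The cost is a few numbers and a unit in one paragraph. No change to sample size, data collection or analysis follows. The stated precision becomes much less favourable than 0.086, and with t it is also slightly less favourable than the printed interval.
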